9.4 Correlative Science Studies

9.4.1 Tumor PD-L1 Expression

Baseline and on-treatment PD-L1 expression will be tested; exploratory analysis will be conducted to correlate PD-L1 (double staining for PD-1 and other markers) with clinical response and immunogenicity.

Correlative study design: The effect of tumor PD-L1 expression on treatment response to anti-PD-1 targeted immunotherapy is currently unclear and a matter of ongoing investigation. Identification of predictive biomarkers of response to therapy protects patients from exposure to risks of ineffective therapies and improves cost-effectiveness. FFPE tumor samples (blocks) will be available for all patients, from dedicated research biopsies at the three timepoints specified. Analysis of PD-L1 expression will be performed by the 22-C3 antibody to PD-L1 by the Qualtex laboratory. PD-L1 membrane staining will be assessed by light microscopy. Either complete circumferential or partial linear plasma membrane staining will constitute positive PD-L1 staining. While cytoplasmic staining may be observed, it will not be used in the evaluation of tissue sample status. Two cut-off values of $\geq 1\%$ and $\geq 50\%$ tumor cell membrane staining will be reported as positive.

Hypothesis: Patients with PD-L1 “positive” or “high H-score” tumors will have an improved PFS in comparison to patients with PD-L1 negative tumors. Double staining of PD-1/PD-L1 will correlate better with outcome than single marker(s).

9.4.2 Tumor Antigen (EGFR, p53, E6, E7) Seroreactivity

Correlative study design: Patients who are seropositive to tumor-specific antigens may derive greater benefit from checkpoint inhibitors. In the case of melanoma, preliminary data indicate that patients with pre-existing antibodies to tumor-specific antigens (e.g. NY-ESO-1, an antigen expressed in 30-40% of patients with advanced melanoma) have an increased response to ipilimumab.³⁷ Approximately 30-40% of patients with HNSCC have detectable titers to EGFR, p53 etc. at diagnosis, indicating immune exposure to these tumor-specific antigens. Seropositivity therefore may be a biomarker for PD-1/PD-L1-mediated suppression of the T cell immune response to these tumor-specific antigens that also are necessary for the malignant phenotype of HPV-negative tumors. Likewise, in patients with HPV-positive tumors, antibodies against E6 and E7 can be observed. Serum samples at enrollment and follow up will be evaluated for the presence of EGFR, p53, E6, E7, etc. seroreactivity by use of a multiplex luminex assay utilizing GST N-terminal tagged proteins covalently bound to microspheres. The assay has been developed as a collaboration between the [name] laboratory and that of [name]/[name] group (German Cancer Research Institute, Heidelberg). Results will be reported as positive or negative based on mean fluorescent values (MFI) in comparison to positive and negative controls.

Hypothesis: Patients who are seropositive to EGFR, p53, E6, E7 and other tumor antigen-specific antibodies will have an improved PFS when treated with pembrolizumab in comparison to patients who are seronegative.

9.4.3 Peripheral Blood CD69/137+ or ICOS+ Activated T cells

Correlative study design: Activated T cells expressing markers CD69 and/or CD137 have been identified in the circulation of head and neck cancer patients but at a low level.^{17,38,39} These cells would be expected to increase after pembrolizumab, reversing T cell “exhaustion” and enabling their reactivation. This detectable population will be measured at baseline and longitudinally in the control and pembrolizumab-treated cohorts. Within this subset of activated, circulating T cells, we will phenotype them by memory/naïve status (using markers CD45Ra and CCR7) according to the patient’s HLA type. Activated T cells expressing markers CD69, ICOS, and/or CD137 will be measured at baseline and longitudinally by use of flow cytometry. We also will secondarily measure memory status, EGFR and p53, and other antigen specificity and PD1-positivity within this population of circulating T cells using flow cytometry.^{17,38-40} Pre-post comparison of these frequencies will be performed for each patient during therapy,

using each patient's baseline as the control time point, and comparing the kinetics of these values in patients treated with sequential vs. concurrent pembrolizumab during CRT.

Hypotheses: Intra-patient increase in the number of activated, CD69+ and/or CD137+ T cells will increase during CRT, between baseline and end-of-CRT blood draw. We also hypothesize that a significant intra-patient increase in the activation markers CD69 and CD137 will be observed.

9.4.4 Tumor Cell Immune Escape, Extent of Tumor Infiltrating Lymphocytes (“Immunoscore”), and Activating/Suppressive Ligands

HLA and antigen loss variants and expression levels will be investigated in tumor tissues, focused on HLA class I, antigen processing machinery (APM) components.⁴¹ Next generation sequencing of tumors will analyze for HLA, beta-2-microglobulin, TAP1/2 and other APM component mutations as recently published.⁴² Immunohistochemistry (IHC) will be used to assess the number and composition of immune infiltrates (“immunoscore”) in order to define the immune cell subsets present within FFPE tumor tissue before exposure to therapy. These IHC analyses will include, but not necessarily be limited to, the following markers: CD4, CD8, FOXP3, PD-1, PD L1, and PD-L2.

9.4.5 Whole Exome Sequencing and RNA-Seq Analysis

To define the neo-epitope landscape and to delineate alterations in transcriptomic signatures we will complete whole exome sequencing (WES) and RNA-Seq on all protocol patients. WES will be performed on baseline tumor samples and DNA from corresponding peripheral blood samples. Somatic mutations and candidate neo-antigens generated from these mutations will be characterized. Neo-antigen prediction will be performed using HLA binding algorithms.^{43,44} RNA-Seq analysis will be performed in matched baseline and Week 2 of CRT biopsies, so the patient's baseline tissue serves as his/her own control. The goal of these studies is to describe the baseline mutational burden and neo-epitope landscape, and to identify changes in RNA-Seq defined transcriptomic signatures. Associations with clinical response and PFS will be evaluated. In particular, RNA-Seq data will highlight which of the predicted neo-epitopes are expressed during CRT alone as compared to patients treated with CRT and concurrent pembrolizumab. These data will describe the immunomodulatory role of CRT distinct from the addition of pembrolizumab and will provide powerful biomarker insight into the potential value of concurrent vs. sequential treatment.

9.4.6 Paired Analysis of TCR Clonality in Pre- and Post-Treatment Tumor Specimens

To define the alterations in TCR clonality between matched baseline and Week 2 CRT biopsies from this trial, we will use the ImmunoSeq assay from Adaptive Biotechnologies to sequence TCR beta chains (as performed previously by the [name] laboratory). The goal of these studies is to examine oligoclonal expansion of T cell subsets and correlate these with clinical outcomes. Clonotypic expansion is a biomarker for a tumor-specific immune response in the absence of knowing tumor antigens of interest a priori.

9.4.7 Germline DNA Analysis for SNPs

To evaluate for and compare variations in DNA that may increase likelihood of prolonged progression-free survival in the context of pembrolizumab plus cisplatin-IMRT for PULA HNSCC, we will isolate DNA from whole blood samples drawn at baseline for single-nucleotide polymorphism (SNP) analysis.

9.4.8 Cryopreserved PBMC will be kept in 10% DMSO in liquid nitrogen for analysis of strength and breadth of HPV16 E6/E7-specific T cell responses by a validated interferon γ Elispot assay. This assay will be performed to assess responses to ISA101b. In addition it will be informative to evaluate differences in HPV16 E6/E7-specific immune responses between long term clinical responders and low/non clinical responders. In HLA-A2+ patients the level of tetramer+ CD8+ T cells will be evaluated. In addition, if sufficient cryopreserved PBMC are available, poistive IFN γ Elispot assyas will be followed by intracellular cytokine staining assayed by intracellular cytokine staining in flow cytometry of CD4+ and CD8+ T cells.

10. STATISTICAL METHODS

This is a single arm phase 2 trial evaluating the efficacy of the addition of the ISA101b to pembrolizumab plus standard cisplatin-RT in intermediate risk HPV-16+ PULA HNSCC. This study is being performed in order to evaluate the oncologic efficacy of ISA101b with pembrolizumab and CRT and to characterize the safety profile of the combination.

10.1 Objectives

Primary Objective:

To estimate two year progression-free survival of the combination of ISA101b, pembrolizumab and cisplatin-based CRT in intermediate risk HPV positive patients and to decide if the outcome warrants further investigation of the combination when compared to the current standard of care (CRT) for this patient population.

Secondary Objective:

- To evaluate the toxicity of the combination of pembrolizumab and ISA101b and concurrent cisplatin-IMRT in patients with PULA HPV-16+ “intermediate risk” HNSCC

10.2 Sample Size

Sample size is determined by the primary objective of testing whether the addition of ISA101b+ pembrolizumab improves two year progression-free survival in HPV-16+ OPSCC patients treated with cisplatin CRT. The historical control for the study is based part upon the results of O’Sullivan and Huang⁴⁵ in which the probability of 3 year OS was approximately 65% for high risk (Class III, T4 or N3, age < 70) HPV+ patients treated with chemoradiation and that 3 year OS is an approximation of two year PFS. For the combination of pembrolizumab, ISA101b, and chemoradiation to be considered for further study it is desirable to demonstrate a 25% relative improvement in 2 year PFS from 65% to 81%. We plan to devote 2 years to patient accrual with 1 additional year of follow-up after closing accrual. Using a one-tailed exponential test (using the maximum likelihood estimator for the hazard rate of the exponential distribution) at $\alpha = .10$, 45 patients will provide 87% power to reject the null hypothesis of 65% two year PFS when the underlying two year PFS is 81%. In order to obtain 45 evaluable patients, we will oversample through a total accrual of 50 fully treated patients. Thus, the planned enrollment to this trial is 50 patients.

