1.2 HPV and Head and Neck Cancer Survival

HPV(+) HNSCC is rapidly increasing in incidence.⁷ In the US, two-thirds of patients with oropharynx cancer have HPV(+) tumors. HPV status and pack-years of tobacco exposure are the major determinants of OS in HNSCC, followed by nodal stage.⁸ Based upon HPV status, pack-years and nodal stage, patients with HNSCC can be classified patients into three risk groups having low, intermediate, or high risk of death. This clinical risk classification has framed national clinical trial priorities in PULA HNSCC. Specifically, de-intensification strategies are being tested in patients with low-risk HPV(+) HNSCC whereas intensification strategies are the major unmet need for high-risk HPV(-) and intermediate-risk HPV(+) disease.^{9,10}

Tumor HPV status has been shown to be a strong, independent prognostic biomarker for patients with HNSCC treated with cisplatin- or cetuximab-based RT. Patients with HPV-positive OPSCC have a 58% (HR 0.42, 95%CI 0.27-0.66) reduction in risk of death when compared to patients with HPV-negative OPSCC, after adjustment for other prognostic factors. HPV-positive cancers have been shown to have higher response rates to chemotherapy and CRT, resulting in higher local-regional disease control. Furthermore, the combination of HPV status, pack-years of tobacco smoking, and tumor stage has been shown to classify patients as having a low, intermediate, or high risk of death. Three-year rates of OS were 93% (95%CI, 88.3-97.7) in the low-risk group, 70.8% (95%CI 60.7-80.8) in the intermediate-risk group, and 46.2% (95%CI 34.7-57.5) in the high-risk group. Novel therapies are thus needed in both intermediate and high-risk patients to improve both local-regional control and reduce risk of distant metastases.

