Additional analyses conducted by O'Sullivan, et al. (2013) have indicated that patients with p16-positive OPSCC with T4 or N2C-N3 disease have a high-risk of disease progression, even if tobacco exposure is < 10 pack-years. Therefore, these patients are also considered eligible for this clinical trial. The sample size calculations presented in this protocol consider the outcome of all of these eligible patients based on observations from RTOG 0522. It is important to note that many of the clinical trials investigating the impact of tumor HPV status on survival have utilized a validated surrogate; tumor p16-expression status as measured by immunohistochemistry. P16-expression has been shown to have ~92% sensitivity and ~90% specificity in comparison to the gold standard of expression of high-risk HPV oncogenes E6 and E7. For this trial, to ensure enrollment of productive HPV-infected HNSCC patients, we will require both p16 IHC (>70% positive tumor cells) AND HPV DNA measured by ISH or PCR.

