- 2) Paired analysis of immune-inflammatory markers in tumor and tumor infiltrating lymphocytes in pre- and post-treatment biopsies. Changes in immune-inflammatory markers will reflect immunomodulation by concurrent cisplatin and IMRT, the standard of care for this patient population. Immune-inflammatory markers will include: A) IHC or immunofluorescence to include: CD3, CD8, CD45RO, CD4/FOXP3, PD-L1 (co-stain on Macs), Ki-67; location of cells. B) RNAseq will be done where fresh-frozen tumor is

available.

- 3) Specific immunophenotypic and functional comparison of HPV-16 E6/E7 specific T cells responses using tetramer (for ~ 50% of enrolled patients who express HLA-A2.1), or overlapping E6/E7 peptides, using flow cytometry and IFN γ ELISPOT or cytolytic assays. Analyses will compare HPV specific vs bulk T cell phenotypes and function.
- 4) Seropositivity (circulating antibodies) and cytokines. Circulating antibodies against HPV E6/E7 and other viral tumor antigens, and circulating cytokines will be analyzed using multiplex (Luminex) ELISA assays.
- 5) Paired analysis of peripheral blood immune-inflammatory markers pre- and post-treatment with pembrolizumab. Markers will include: multi-color flow cytometry, including T cell activation panel, NK cells, myeloid-derived suppressor cells (MDSC), Treg subsets, phenotypic subsets, expression of PD1 and other co-stimulatory/co-inhibitory markers on these specimens.
- 6) Paired analysis of TCR clonality will be conducted in pre- and post-treatment TILs.
- 7) Next generation sequencing (exomes) for genomic epitope mapping with HLA allelic typing. Further detail is given in Section 9.4.5.

Summary of Rationale

- Data from the RTOG 0522, inclusive of the patients who meet the eligibility criteria for this trial, indicates that 30-40% of patients with intermediate risk, local-regionally advanced HPV+ HNSCC will experience disease progression within 5 years of CRT. Novel therapeutic approaches are needed to improve disease control (Ang 2010, O’Sullivan 2013).
- Anti PD-1 targeted therapy (pembrolizumab, Merck Inc.) demonstrated activity in metastatic recurrent HNSCC, with a response rate of 20% in patients with HNSCC (Seiwert 2014) Eligibility criteria included 1% or greater PD-L1 expression on tumors. Response rates were different for patients with high versus low PD-L1 expression (45% versus 11%).

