2.3 Exploratory

- To evaluate associations between tumor PD-L1 expression and PFS and OS in patients treated with pembrolizumab and ISA101b; PD-L1 status will not be used during this trial for treatment decisions
- To evaluate the safety, feasibility and patient compliance with continued administration of single agent pembrolizumab 200 mg IV q21 days for 14 further doses after completion of chemoradiation with concomitant pembrolizumab
- To evaluate associations between HPV E6/E7 seroreactivity and PFS in p16-positive patients treated with and without pembrolizumab and therapeutic ISA101b
- To evaluate the frequency and functional phenotype of HPV-16 E6 and E7 specific circulating activated, PD-1+ T cells in patients treated with and without pembrolizumab
- To evaluate the dynamics of PD-L1 expression in the tumor and TILs via a repeat biopsy after 2-3 weeks after pembrolizumab and ISA101b vaccination in patients with accessible tumor.
- To evaluate the tumor microenvironment, activation, and proliferation markers on TIL and NK cells in pre- and post-treatment specimens, including CD3, CD8, CD45RO, CD4/FOXP3, PD-L1, and Ki-67
- To evaluate the dynamic expression of TA-specific T cells in serial peripheral blood mononuclear cells (PBMCs) by flow cytometry

3.

PATIENT SELECTION

3.1

Inclusion Criteria

Each patient must meet all of the following inclusion criteria to be enrolled in the study:

- Patients must have histologically-confirmed head and neck squamous cell carcinoma with no evidence of distant metastasis. The primary site will be the oropharynx. Patients with squamous cell carcinoma of unknown primary, metastatic to cervical lymph nodes, are permitted to enroll provided all other eligibility criteria are met.
- Patients must have intermediate risk disease, defined below. Staging evaluation should be determined by imaging studies and complete head and neck exam in accordance with the American Joint committee on Cancer Staging Manual, 7th edition.
 - Patients must meet one of the following criteria:
 - Oropharynx: p16(+) PLUS HPV ISH(+) AND one of the following
 - T3 OR \geq N2a AND \geq 10 pack-years tobacco exposure (see Tobacco Assessment Form, Appendix A)
 - T4 or N2c/N3 disease irrespective of tobacco exposure
 - Unknown primary: p16(+) PLUS HPV ISH(+) AND one of the following
 - \geq N2a AND \geq 10 pack-years tobacco exposure

- N2c/N3 disease irrespective of tobacco exposure

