10.4 Proposed Data Analysis

At study completion a one-sided one sample exponential test will be conducted to detect an increase above the presumed historical control rate of 65% PFS at two years. If this test is rejected at $\alpha = .10$, the treatment regimen will be considered sufficient for further investigation. Probabilities of times to local recurrence, regional recurrence and death will be estimated by the Kaplan-Meier method with 95% confidence intervals as well as by cumulative incidence if needed to adjust for the competing risk of death. Treatment-related toxicities will be summarized by frequency and grade. If intervening deaths are observed cumulative incidence plots and analysis of competing risks may be conducted.

A series of correlative studies will be conducted based on blood and tissue samples collected prior to treatment among patients treated with pembrolizumab + ISA101b. The first item below is a planned analysis with alpha spending of 10% to be distributed among the biomarker endpoints.

1. Test the association of baseline H score of PD-L1 tumor expression, circulating antibodies against HPV, EGFR and p53 and other tumor antigens upon PFS using proportional hazards regression adjusting if needed for confounding variable such as T stage, N stage and smoking history.
2. Estimate and test the effect of ISA101b using paired (pre/post pembrolizumab +/- ISA101b) values of immune and inflammatory makers will be compared with the Wilcoxon test.
3. Compare differences in circulating HPV, EGFR, p53 and other tumor antigen antibodies using baseline versus 3-6 weeks or 6 months post-treatment. Linear mixed effect models will be used to evaluate the longitudinal response.
4. Estimate and characterize sequential series of blood samples pre- and post-treatment for a series of immune and inflammatory markers. These will be specified by the investigator and due to exploratory nature of these additional tests, p values will be adjusted for false discovery.

The change in CD4, CD8, FOXP3, PD-1, PD L1, and PD-L2 over time will be described graphically. An exploratory analysis of the relationship between those changes and PFS will be conducted by proportional hazards regression.

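### The 65% null comes from a T4/N3 subgroup's 3-year OS and is not tied to the eligible population, so the stated 10% false-positive rate is not secured; at the protocol's own 70.8% it would be 28–35%

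*Combined protocol and SAP*

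**What the plan says.** Section 10.2 derives the historical control from a published risk-group study of chemoradiation, "in which the probability of 3 year OS was approximately 65% for high risk (Class III, T4 or N3, age < 70) HPV+ patients". It describes the control as resting only in part on that study, but gives no other part. It then takes 3-year OS as an approximation of 2-year PFS, without support.

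Section 1.2 describes the basis differently: "The sample size calculations presented in this protocol consider the outcome of all of these eligible patients based on observations from RTOG 0522". No RTOG 0522 figure appears in Section 10.2. Section 1.2 also reports a 3-year OS of "70.8% (95%CI 60.7-80.8) in the intermediate-risk group", and intermediate risk is the label the objectives and Section 10 give to this trial's population.

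Eligibility in Section 3.1 is wider than T4/N3. For oropharyngeal primaries it admits "T3 OR \geq N2a AND \geq 10 pack-years tobacco exposure", and also T4 or N2c/N3 disease at any smoking level. The benchmark's limit of age under 70 is not an entry criterion.

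On the test, Section 10.2 states: "Using a one-tailed exponential test (using the maximum likelihood estimator for the hazard rate of the exponential distribution". The design claim is that "45 patients will provide 87% power to reject the null hypothesis of 65% two year PFS when the underlying two year PFS is 81" per cent. Section 10.4 sets the decision rule: "If this test is rejected at $\alpha = .10$, the treatment regimen will be considered sufficient for further investigation". Section 10.5 uses the same 65% for futility monitoring.

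**The concern.** In a single-arm trial the null value stands in for the control arm. The 10% error rate in Sections 10.2 and 10.4 holds only if 65% is what chemoradiation alone would achieve in the patients enrolled. The cited benchmark describes a group that Section 10.2 itself calls high risk, while the trial describes its population as intermediate risk and reports a higher survival figure for that category. If the true control rate is above 65%, the regimen can be declared worth further investigation without adding anything, and the estimate would inform the later randomised trial named in Section 2.1. A null that is too low would also make the Section 10.5 futility rule less likely to stop the trial.

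**Working it through.** **Inputs.** From Section 10.2: 45 evaluable patients, one-sided alpha 0.10 (z = 1.2816), null 65%, alternative 81%, 2 years of accrual (assumed uniform) and 1 further year of follow-up. The exponential model is the plan's own; Section 10.5 gives the null hazard as 0.215 per year.

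**Formulas.** With S the 2-year PFS:
- hazard: λ = −ln(S)/2
- event probability: p = 1 − [exp(−λ) − exp(−3λ)]/(2λ)
- pass probability, hazard scale: Φ{[λ0 − z·λ0/√(n·p0) − λ] / [λ/√(n·p)]}
- pass probability, log-hazard scale: Φ{[ln(λ0/λ) − z/√(n·p0)]·√(n·p)}

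**Step 1: reproduce the plan.** λ0 = 0.2154 and λ1 = 0.1054, with 15.5 and 8.5 expected events. The critical hazard is 0.2154 − 1.2816 × 0.2154/√15.52 = 0.1453, so the trial passes when fitted 2-year PFS is at least exp(−2 × 0.1453) = 74.8%. Power is Φ[(0.1453 − 0.1054)/(0.1054/√8.48)] = Φ(1.10) = 86.5%, or 87.2% on the log scale. The stated 87% reproduces, so the arithmetic is sound and the question is the null.

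**Step 2: true control rate 70.8%.** λ = 0.1727, with 13.0 expected events.
- Hazard scale: Φ[(0.1453 − 0.1727)/(0.1727/√12.98)] = Φ(−0.57) = 28%.
- Log scale: Φ[(0.221 − 0.325) × 3.60] = Φ(−0.37) = 35%.
- Simulation with four versions of the test gives 29–32%.

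**Step 3: pass probability when the regimen adds nothing.**

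| True 2-year PFS on chemoradiation | Hazard scale | Log scale |
|---|---|---|
| 60.7% (lower CI limit) | 4% | 2% |
| 65% (plan's null) | 10% | 10% |
| 70% | 25% | 31% |
| 70.8% (intermediate-risk figure) | 28% | 35% |
| 75% | 51% | 60% |
| 80.8% (upper CI limit) | 86% | 87% |

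**Step 4: the same 45 patients judged against 70.8%.** The critical hazard is 0.1727 − 1.2816 × 0.1727/√12.98 = 0.1112, a fitted 2-year PFS of 80.1%. Power at a true 81% is Φ[(0.1112 − 0.1054)/(0.1054/√8.48)] = Φ(0.16) = 56%, or 66% on the log scale. Restoring 87% on the hazard scale would take about 104 patients. A fitted 2-year PFS between about 75% and 80% would therefore exclude 65% but not 70.8%.

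**The case against.** Four points can be made for the plan.

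- The 70.8% is OS in a published risk group, not PFS in this eligible mix, and its confidence interval includes 65%. This stands. The figure shows that 65% is not the only value the protocol supports, not that 65% is wrong.
- The direction of any case-mix difference is not shown. The additional T3 and N2a–N2b patients must have at least 10 pack-years, which Section 1.2 treats as a major adverse factor. Section 1.2 groups N2c with T4 and N3 as high risk, and lifting the age limit could lower outcomes. This also stands: a reader might infer that case mix alone would produce a positive result, but the documents give no stage- or smoking-specific PFS to support that.
- Section 10.2 claims the subgroup only as part of its basis. That is fair, but the rest is not documented, and the statement about RTOG 0522 in Section 1.2 is not carried through.
- Passing the test leads only to further investigation, and the trial also aims to estimate PFS. This limits the consequence but does not restore the 10%.

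A stronger reading is tempting. The Summary of Rationale says that "30-40% of patients with intermediate risk, local-regionally advanced HPV+ HNSCC will experience disease progression within 5 years of CRT". Under a constant hazard, 60–70% free of progression at 5 years becomes 0.60^0.4 = 81.5% to 0.70^0.4 = 86.7% at 2 years, which is above the 81% target. A reader might conclude that chemoradiation alone would pass about 89–99% of the time. The documents do not support this. The figure counts progression, while PFS in Section 6.1.3.7 also counts deaths. The conversion depends wholly on the constant hazard: if progression is early, 2-year freedom from progression is near 60–70%, which straddles 65%. It also conflicts with the 70.8%: on the same assumption 2-year OS in that group is 0.708^(2/3) = 79.4%, and PFS cannot exceed OS.

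**Conclusion.** The concern holds in a limited form. Sections 1.2 and 10.2 disagree on the basis of the sample size, and the 65% null is not tied to the Section 3.1 population. If the plan's OS-to-PFS rule is applied to its own intermediate-risk figure, the decision rule passes an inactive regimen 28–35% of the time, about three times the nominal rate. Over that figure's confidence interval the range is about 2–4% to about 86%. These results assume exponential PFS, uniform accrual, 45 evaluable patients and the unsupported equation of 3-year OS with 2-year PFS. They do not show that 65% is too low, and the 5-year progression figure does not settle the matter either way. They show that the stated 10% is conditional on a value the protocol has not justified.

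**What to change.** 1. Reconcile Sections 1.2 and 10.2. State the basis of the null for patients meeting Section 3.1, including whatever source besides the T4/N3 series was used.
2. If 65% is kept, add to Section 10.2 the pass probability over true control rates of about 61–81%: 10% at 65%, 28–35% at 70.8% and 51–60% at 75%. State also that power against 70.8% is about 56–66% at a true 81% with 45 patients.
3. In Section 10.4, report the one-sided 90% lower bound for 2-year PFS against 70.8% as well as 65%. Qualify the conclusion that the regimen merits further study when only 65% is excluded, which on the hazard-scale test means a fitted 2-year PFS of about 75–80%.

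Replacing the null outright with 70.8% is not required. It would leave the primary test underpowered at the planned size and would again rest on OS from a group that does not match eligibility exactly.

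The cost is protocol and SAP wording and a less favourable stated power. No extra patients or procedures are needed.
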